Whole mount pathologic analysis of PET imaging in prostate cancer has been reported primarily out of Germany. No prospective trials were found combining PSMA, PET-CT, and whole-mount analysis. Furthermore, studies have focused on high-risk disease rather than low/intermediate risk. For example, a retrospective trial out of Germany (Eiber, et al. 2016) combined Ga-PSMA-11 and PET-CT and found improvement in Receiver operator curve (ROC) for PET-CT over MRI (0.73 to 0.88, p<0.001). Of the 53 patients, 53% were high risk. The authors concluded prospective studies were warranted for biopsy guidance. Recently, F-FACBC (Fluciclovine) was used with PET-CT and compared to MRI for biopsy guidance in a prospective clinical trial (Jambor, et al. 2017). F-FACBC had high sensitivity (87%), but low specificity (56%) resulting in a low ROC (0.72). F-FACBC is not specific for prostate cancer resulting in replacement with PSMA-based tracers in clinical practice.

[figure not shown]
The Urology-Radiology-Pathology team at Indiana University has been employing fusion biopsy since 2013 and has performed more than 600 during this time. A recent abstract presented at the annual meeting of the American Urologic Association in 2017 demonstrated 22% of index lesions (largest tumor) were missed by MRI ([name], et al. 2017), and MRI undersized the index cancer lesion when compared to final pathology (2.2cm vs. 1.9cm, p = 0.03). A tracer that is both more sensitive and specific is desired leading urologists to continue ultrasound template biopsies with MRI targeted biopsy.

The Ga-PSMA-11 (HBED-CC) radiopharmaceutical (Eder, et al. 2014; Eiber, et al. 2015, Afshar-Oromieh, et al. 2015) is structurally based on a class of urea-derived inhibitors of PSMA (Pillai, et al. 2016). The targeting peptide has been modified at its N-terminus to incorporate the HBED-CC chelating agent with an exceptionally high binding affinity (~1039) for the Ga3+ ion (Figure 1 and Table 1). Methods for on-demand

production of  $^{68}\text{Ga}$ -PSMA-11 are already established (IND # 131,806), based on our research use of this radiopharmaceutical in imaging patients with recurrent prostate cancer.

**Table 1.** PSMA Affinities of the PSMA-11 Agent Before, and After,  $\text{Ga}^{3+}$  Chelation

PSMA Ligand	IC50 (nM)
PSMA-11 HBED-CC	$5.7 \pm 0.5$
Ga-PSMA-11 HBED-CC	$6.1 \pm 0.8$

[figure not shown]

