### 9.3 Sample Size

Table 1: Sample size calculation:

	sensitivity= 0.80	sensitivity= 0.85	sensitivity= 0.90	sensitivity= 0.95
Error allowed (d)= 7.5%	46	37	27	14
Error allowed (d)= 10%	27	21	15	8

Our sample size is based on the key primary endpoint of sensitivity to detect clinically significant (Gleason >6 and >5mm) cancer overall. In the Table above we summarized the sample size required to achieve a certain degree of accuracy for different sensitivity levels. All the calculations are based on the normal approximation of the binomial distribution. For this pilot, we will also assume the samples within each patient are independent statistically. Each patient has six samples for diagnostic testing (sextants) and the prevalence of cancer per sextant is estimated to be 40% (Eiber et al., 2016). The rows (d) present the marginal maximal error under 95% confidence interval and the columns represent the sensitivity rate. The numbers in Table 1 represent the required number of patients needed for each different combination of marginal error (d) and sensitivity rate. In other words, for a sensitivity of 90% and a marginal error of 7.5%, we

are 95% sure that the sensitivity lies between 82.5% and 97.5% if we enroll 27 patients. Based on Table 1, the maximal sample size is 46 assuming the sensitivity is 80%. Therefore, we decided 36 patients was adequate to ensure that the proposed trial can achieve certain accuracy of the sensitivity across the majority the scenarios considered in Table 1.

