## 9.4 Study Endpoints

### 9.4.1 Primary

Sextant based analyses using prostatectomy whole-mount analysis or biopsy as Gold Standard (Appendix D):

- Sensitivity, specificity, Receiver operator curve (ROC) of mpMRI overall and for each Gleason pattern (3, 4, 5)
- Sensitivity, specificity, ROC of PSMA PET-CT overall and for each Gleason pattern (3, 4, 5)

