## **9.7 Analysis of Primary Objective**

We will use the generalized estimation equation (GEE) to fit the data and estimate the sensitivity and specificity. We will use the receiver operating characteristic (ROC) curve to represent the values of sensitivity and specificity at different thresholds (PET= SUV, mpMRI=suspicion scores). According to the ROC curve, we will determine the optimal threshold with a minimal sensitivity of 50% by maximizing the Youden index. We will use the McNemar test to compare the sensitivity and specificity values between PET and MRI although data from this pilot study is considered hypothesis generating only due to the small sample size. In addition, we will use the bootstrapping method to detect the significant difference of the area under curve (AUC) with different ROC curves.

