## **9.8 Analysis of Secondary Objectives**

The proportion of patients who had cancer detected by both the standard of care imaging (MRI) and the Ga-PSMA-11 PET imaging will be calculated, along with exact 95% confidence intervals. A similar approach will be used for other secondary outcomes in Section 9.4.2 to compare the cancer detection of the mpMRI and Ga-PSMA-11 detection method to the surgical observations and the clinical tissue histopathology findings.

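### The PET-versus-MRI comparison in section 9.7 applies an unclustered McNemar test to sextants, so its p-values are too small if PET-minus-MRI differences correlate positively within a patient

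*Combined protocol and SAP*

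**What the plan says.** Section 9.4.1 sets the unit of the primary analysis: "Sextant based analyses using prostatectomy whole-mount analysis or biopsy as Gold Standard". Appendix D confirms it and lists the six sextants.

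Section 9.7 then gives two methods for the same sextant data. For estimation: "We will use the generalized estimation equation (GEE) to fit the data and estimate the sensitivity and specificity". For the PET-versus-MRI comparison: "We will use the McNemar test to compare the sensitivity and specificity values between PET and MRI". It names no clustered form of the test, no reduction to one pair per patient and no test taken from the GEE model. It also does not say whether McNemar is uncorrected, continuity-corrected or exact. The same sentence describes the data as hypothesis generating because the sample is small.

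Section 9.3 assumes independence for the sample size: "we will also assume the samples within each patient are independent statistically". That section gives six sextants per patient, 40% prevalence per sextant and 36 patients.

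**The concern.** McNemar's variance counts each discordant sextant as a separate piece of evidence. If a patient's discordant sextants tend to point the same way, for example PET positive and MRI negative in several at once, the true variance of the net difference is larger than the test assumes and the p-value is too small.

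The protocol gives a reason to expect this. Section 3.1 reports from the site's own series that "MRI undersized the index cancer lesion when compared to final pathology (2.2cm vs. 1.9cm, p = 0.03", so the index lesion averaged 2.2 cm on pathology. If a sextant is one third of a gland assumed to be 4-5 cm long, it measures 1.3-1.7 cm, and a 2.2 cm lesion can cross a boundary. When one modality misses such a lesion and the other finds it, neighbouring sextants become discordant in the same direction.

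At stake is how the reported comparison is read. The GEE intervals and the McNemar p-value for the same sextants could disagree because they rest on different assumptions, and an overstated difference could carry into the larger trials that this pilot is meant to inform.

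**Working it through.** **1. The plan's own figure.** Table 1 in section 9.3 follows from n = 1.96² × p(1−p)/d² sextants, divided by 6 × 0.40 = 2.4 positive sextants per patient and rounded up. For p = 0.80 and d = 0.075, n = 109.27, and 109.27/2.4 = 45.53, so 46 as stated. The full row for 7.5% comes out as 46, 37, 26, 14 (stated 46, 37, 27, 14). The row for 10% comes out as 26, 21, 15, 8 (stated 27, 21, 15, 8). The table therefore contains no design effect, as section 9.3 says. The documents give no alpha or power for the McNemar comparison; I take two-sided 5%.

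**2. What matters for the test.** Let ρ be the within-patient correlation of the difference PET minus MRI among sextants of the same disease status. It is not the correlation of each modality's own results. With cluster size M distributed Bin(6, prevalence), the variance inflation is DE = 1 + (E[M²]/E[M] − 1)ρ.

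- Sensitivity: E[M²]/E[M] = (1.44 + 2.4²)/2.4 = 3.0, so DE = 1 + 2ρ.
- Specificity: (1.44 + 3.6²)/3.6 = 4.0, so DE = 1 + 3ρ.

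The true size is 2 × [1 − Φ(1.96/√DE)].

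| ρ | DE, sensitivity | Size | DE, specificity | Size |
|---|---|---|---|---|
| 0 | 1.0 | 5.0% | 1.0 | 5.0% |
| 0.1 | 1.2 | 7.4% | 1.3 | 8.6% |
| 0.3 | 1.6 | 12.1% | 1.9 | 15.5% |
| 0.5 | 2.0 | 16.6% | 2.5 | 21.5% |

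**3. From each modality's ICC to ρ.** Suppose both modalities have the same accuracy and the same ICC, and their patient effects correlate by r. Then ρ = ICC(1 − r)/(1 − r × ICC). With r = 0, ρ equals the ICC. With r = 0.5 and ICC 0.3, ρ = 0.15/0.85 = 0.18. With r = 1, ρ = 0 and McNemar is valid.

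**4. Simulation.** 10,000 trials per setting, 36 patients, positives per patient Bin(6, 0.40), true accuracy 80% for both modalities, beta-distributed patient detection probabilities. Each cell gives the size of a nominal 5% test at ICC 0 / 0.1 / 0.3 / 0.5.

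| Patient effects | Test | Sensitivity | Specificity |
|---|---|---|---|
| Specific to each modality | McNemar, uncorrected | 5/7/12/17% | 5/8/15/22% |
| Specific to each modality | McNemar, exact | 3/5/9/13% | 4/6/12/18% |
| Correlated 0.5 (Gaussian copula) | McNemar, uncorrected | 5/7/10/14% | 5/7/12/18% |
| Fully shared | McNemar, uncorrected | about 5% | about 5% |

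The clustered statistic (Σdᵢ)²/Σdᵢ², with dᵢ the patient's net discordance, stays at about 5% in all of these settings.

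**5. Lesion mechanism without any ICC.** Each lesion is found or missed whole, with probability 0.80 per modality. The sensitivity test has size 5% if every lesion fills one sextant. With positives per patient held close to 2.4, it has size 9% if 40% of patients have one two-sextant lesion and 16% if every patient has one. With Bin(6, 0.40) positives, where some patients have too few positive sextants to hold such a lesion, the last two figures are 8% and 13%.

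**The case against.** **Consequence.** The plan labels the comparison hypothesis generating, sizes the trial on the precision of sensitivity, and attaches no alpha or decision to the test. This stands and limits the harm. It does not correct the p-value.

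**The upper figures need strong assumptions.** Both modalities image the same glands, so part of the patient effect is probably shared. With patient effects correlated 0.8 between modalities, uncorrected McNemar had size 6.1% and 7.6% for sensitivity, and 5.7% and 8.2% for specificity, at ICC 0.1 and 0.3. With full sharing there is no inflation. This stands: the documents give neither an ICC nor a cross-modality correlation.

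**Test version.** Exact and continuity-corrected McNemar are conservative at these counts. With modality-specific effects at ICC 0.1 they are at about 5% for sensitivity and 6-7% for specificity. At ICC 0.3-0.5 they still exceed 5% clearly. Section 9.7 does not choose a version.

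**Mechanism.** The lesion-span argument bears on sensitivity only. It uses the largest lesion and needs a gland length that the protocol does not give. The 22% is for specificity, for which the protocol offers no comparable mechanism.

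**Not the whole procedure.** Section 9.7 chooses thresholds by the Youden index in the same data. The simulation fixes accuracy, so it isolates the effect of clustering and does not give the overall error rate of the planned analysis.

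The disclosed independence assumption in section 9.3 is not an answer: it supports the sample size and does nothing to the test.

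**Conclusion.** The concern holds in its conditional form. Section 9.7 specifies a test for independent pairs on data with about 2.4 or 3.6 relevant sextants per patient, and no section supplies a patient-level adjustment. If PET-minus-MRI differences correlate positively within patients, the nominal 5% test is anti-conservative: 7-17% for sensitivity and 8-22% for specificity at modality-specific ICC 0.1-0.5, less when the patient effect is partly shared, and 5% when it is fully shared. Only the 40% prevalence, the six sextants and the 36 patients come from the plan. The ICCs, the 80% accuracy, the lesion spans and the two-sided 5% level are assumptions. The missing adjustment is certain; the size of its effect is not. It should be fixed, but nothing else in the design depends on it.

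**What to change.** State in section 9.7 that the PET-versus-MRI comparison is clustered on patient, and replace McNemar with one of the following:

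- a GEE contrast for modality, fitted separately within positive and negative sextants, with patient as the cluster and a robust variance with small-sample correction. This matches the estimation method already planned;
- a clustered McNemar test (Obuchowski or Durkalski).

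In simulation with modality-specific effects and ICC 0-0.5, size was 4.8-5.4% for the GEE contrast, 4.1-4.5% for Obuchowski and 4.6-5.0% for Durkalski, against 5.0-21.6% for ordinary McNemar.

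Two clarifications fit in the same edit. Say that the AUC bootstrap resamples patients, since section 9.7 names no unit. If the approach of section 9.8 is extended to lesion-level accuracy, use patient-clustered intervals there and keep exact intervals for proportions of patients.

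The cost is SAP wording, a few lines of code and some apparent power. For 90% versus 80% sensitivity with no clustering, power falls from 46% (McNemar) to 44% (GEE contrast), 41% (Obuchowski) or 37% (Durkalski). At modality-specific ICC 0.3 it is 28-31%, against a nominal 47% for McNemar that comes with a 12-13% false-positive rate. No new patients, data or procedures are needed.

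### As section 9.7 reads, McNemar compares PET and MRI at separately estimated Youden cut-offs as if these were known, so scans with the same ROC curve would often be reported as different

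*Combined protocol and SAP*

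**What the plan says.** Section 9.7 sets out the analysis in consecutive sentences. ROC curves are drawn "at different thresholds (PET= SUV, mpMRI=suspicion scores"). Then "we will determine the optimal threshold with a minimal sensitivity of 50% by maximizing the Youden index". The next sentence reads "We will use the McNemar test to compare the sensitivity and specificity values between PET and MRI", and continues "although data from this pilot study is considered hypothesis generating only due to the small sample size". The last sentence adds a bootstrap comparison of AUCs.

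For the McNemar comparison, 9.7 gives no cut-off fixed in advance, no resampling that repeats the cut-off choice, no significance level and no multiplicity rule. Bootstrapping is mentioned only for the AUC.

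The sample-size text in 9.3 supplies the design figures: "we decided 36 patients was adequate", six sextants per patient at 40% prevalence, and "we will also assume the samples within each patient are independent statistically". The only MRI and PSMA-PET AUCs in the document are in section 3.1: 0.73 and 0.88, from a cited retrospective study.

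**The concern.** McNemar's null distribution holds when each sextant's positive or negative call comes from a rule set beforehand. Discordant pairs then split like a fair coin if the two rules have equal sensitivity (or specificity). In 9.7 the rule for each scan is itself an estimate, found separately for SUV and for the MRI suspicion score. Because the Youden index changes little around its maximum, the estimated cut-off can lie well to either side of the true optimum. One scan may end up with high sensitivity and low specificity and the other with the reverse, although their ROC curves are identical. An ordinal MRI score adds to this, because its few possible cut-offs may not include the PET operating point.

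What is at stake is the only planned test of PET against MRI on sensitivity and specificity. A typical result would be that PET is significantly more sensitive and MRI significantly more specific, when all that differs is where the two cut-offs happened to fall. The trial's exploratory aim is to feed later, larger studies, and such a finding could be carried into their design.

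**Working it through.** **Inputs from the plan.** 36 patients (9.3); six sextants each, 40% positive, independent (9.3); Youden maximum with sensitivity of at least 50% (9.7); AUC 0.73 to 0.88 (3.1). Expected positive sextants: 36 × 6 × 0.40 = 86.4. Expected negative sextants: 36 × 6 × 0.60 = 129.6.

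**Assumptions not in the plan.** Two-sided 5% for each McNemar test; the exact version unless stated; binormal scores of equal variance; between-scan correlation (ρ) as shown.

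**Plan's own figure first.** Table 1 in 9.3 follows from n = 1.96² × p(1 − p) / d² / (6 × 0.40), rounded up. For p = 0.80 and d = 0.075: 3.84 × 0.16 / 0.005625 / 2.4 = 45.5, so 46. The eight cells come out as 46, 37, 26, 14 and 26, 21, 15, 8. The plan prints 27 in the two cells where I get 26; otherwise they agree. The design inputs are therefore read correctly. The plan states no error rate for McNemar, so there is none to reproduce.

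**Simulation under equal accuracy.** Both scans have the same AUC; positives are shifted by √2 × Φ⁻¹(AUC). Each scan's cut-off is its own in-sample Youden maximum. McNemar is run on positive sextants (sensitivity) and negative sextants (specificity). Share of trials with at least one p < 0.05 (4,000 trials per cell):

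| AUC of both scans | ρ = 0 | ρ = 0.3 | ρ = 0.5 | ρ = 0.7 |
|---|---|---|---|---|
| 0.73 | 48% | 52% | 54% | 58% |
| 0.80 | 44% | 46% | 50% | 51% |
| 0.88 | 33% | 37% | 39% | 43% |

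Over this grid the sensitivity test alone rejects in about 17–41% and the specificity test alone in about 26–51%. The asymptotic McNemar gives 39–63% for at least one.

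**Comparator.** With both cut-offs fixed at the true optimum and the same kind of data, at least one exact test rejects in about 6–7%. Two independent tests at exactly 5% would give 1 − 0.95² = 9.75%.

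**Why the rate rises.** At AUC 0.80 the standard deviation of the sensitivity difference is 0.12 with estimated cut-offs and 0.06 with fixed ones. McNemar's reference distribution allows only for the smaller spread.

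**Is reuse of the data the cause?** No. At ρ = 0.3, taking the cut-offs from one sample and running McNemar in a fresh one gives 56%, 50% and 41% at AUC 0.73, 0.80 and 0.88. Testing in the same sample gives 53%, 47% and 38% in the same run.

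**Does size cure it?** No. At AUC 0.80 and ρ = 0.5 the rate is 50% with 36 patients, 60% with 100 and 65% with 360. McNemar gains power to detect the remaining gap between the two cut-offs faster than that gap closes.

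**Sensitivity to the assumptions.**
- MRI as a 5-level score: about 27–66%, depending on where the levels fall.
- Both scans on coarse 5-level scores: 9–20%. The plan uses SUV for PET, so this is not its case.
- Table 1 sensitivities of 0.80, 0.85, 0.90 and 0.95 read as symmetric ROC curves (AUC = Φ(√2 × Φ⁻¹(sensitivity)) = 0.88, 0.93, 0.965, 0.99): about 34–42%, 27–33%, 21–26% and 10–12%.
- Within-patient correlation of 0.3: 35–54% with estimated cut-offs, 11–17% with fixed ones. Clustering is a separate and smaller effect.

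**The case against.** Four points can be made for the plan.

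*The premise is an inference.* Section 9.7 never says that McNemar is run at the Youden cut-offs, and it writes of one optimal threshold. Section 7.3.2 has readers mark suspicious lesions blinded, which could supply yes/no calls without a derived cut-off. This stands as a limit on certainty. Still, the Youden point is the only operating point 9.7 defines, it comes in the sentence before the test, and SUV and suspicion score cannot share one threshold. If the blinded marks are meant, one sentence saying so would remove the problem.

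*The rejections are not all false.* Once two cut-offs sit at different points of one ROC curve, the dichotomised scans do differ in sensitivity and specificity, and McNemar is right to say so. This stands. A reader might infer that the trouble is overfitting from choosing and testing on the same data, or that McNemar has a 35–55% type I error for its own null. Neither is supported: the rate does not fall in fresh data, so a hold-out sample would not help. What fails is the step from that result to a difference between the scans, because the placement of the cut-offs is noise that the test ignores.

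*The AUC bootstrap already compares accuracy.* True, and it is the better comparison. But 9.7 does not make it the main one or make the McNemar results depend on it.

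*The comparison is labelled hypothesis generating.* No decision rests on it, 9.3 sizes the trial on the precision of sensitivity, and 9.4.1 lists the accuracy of each scan without naming a comparison. This limits the consequence. It does not remove the fault, because the reason given is small numbers, and larger numbers make the rate higher.

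**Conclusion.** The concern holds on the natural reading of 9.7. For two scans of equal AUC in the cited range of 0.73 to 0.88, with continuous scores, ρ of 0 to 0.6 and exact 5% tests, at least one of the two McNemar tests is significant in about 35–55% of trials, against about 6–7% with cut-offs fixed in advance. With a 5-level MRI score the range is about 27–66%, and the rate falls at higher AUCs.

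The size depends on the AUC, the correlation, the McNemar version and the significance level, none of which 9.7 fixes; within the cited AUC range they change the size of the problem but not its presence. The 35–55% is an either-of-two rate, so a reader should not set it against 5%: the fair comparator is 6–7% as simulated, or 9.75% nominally. The cause is that uncertainty in two separately estimated cut-offs is ignored. It should be corrected, but as a pilot comparison it does not undermine the trial's main estimates.

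**What to change.** Amend 9.7 in one of two ways.

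1. State both cut-offs, the SUV and the MRI suspicion score, before unblinding, and run the paired comparison there. The documents name neither value, so the investigators must supply and justify them.
2. Drop McNemar at the Youden cut-offs. Report those sensitivities and specificities descriptively, with a bootstrap interval for each PET–MRI difference that resamples whole patients and re-derives both cut-offs in every resample. In a check at the same equal-accuracy settings this interval was conservative, so it should be expected to be wide.

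A third possibility, not required, is to fix only the MRI cut-off and take PET at the SUV with matching specificity. In simulation its patient-level bootstrap interval rejected in about 4–5% under equal accuracy.

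In either case, name the AUC bootstrap already in 9.7, resampling patients, as the PET–MRI comparison of accuracy. With both scores continuous it rejected in about 6–7% under equal accuracy; it was not checked with an ordinal MRI score. If the blinded lesion marks were always meant to supply the calls for McNemar, say so instead.

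The cost is a few sentences and a short program, with no new patients or data. The downside is fewer nominally significant differences and wider intervals, or the need to commit to cut-offs in advance.
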